### Examination of First and Second Generation E-cigarettes

however, alternative methods may be employed if issues arise with the preferred method (e.g., participant has run out of minutes; cellular providers are not compatible). If participants are unable to complete a daily diary using the link to the online survey, they may be contacted by other methods by Switch study staff to complete the daily diary. If participants become ineligible during the course of the study, compensation for daily diaries will be given only for diaries completed up to the date that they were deemed ineligible. Diary data will provide several outcome variables: 1) Smoking behavior: conventional cigarettes smoked per day and 2) EC use: amount of e-liquid use and frequency of EC use; and 3) EC flavor: report EC flavors used that day (categories for flavors along with examples will be provided).

Table 3. Outcome Measures		Baseline		Randomized Product Trial			Surveillance		
Weeks		-1	0	1	4	8	12	26	52
Self-Report Measures									
Sampling Procedures			X	X	X	X			
Product/Tobacco Use History and Exposure	X								
Demographic History	X								
Daily online e-cigarette and smoking diary	X	X	X	X	X	X	X		X
Timeline Follow-Back	X	X	X	X	X	X	X		X
Cigarette Dependence Scale 2			X	X	X	X	X		X
Cigarette Dependence Scale	X	X	X	X	X	X	X		X
Product Evaluation Scale			X	X	X	X			
Cigarette Evaluation Scale		X		X		X	X		X
Drug Effects/Liking Questionnaire (cigarettes and e-cigarettes)		X		X		X	X		X
Cigarette Purchase Task (cigarettes and e-cigarettes)			X	X	X	X			
E-cigarette product transitions questionnaire			X	X	X	X	X		X
Motivation Rulers (cigarettes and nicotine)	X	X	X	X	X	X	X		X
Biomarker Measures									
Total NNAL (urine)			X		X		X	X	X
Total NNN (urine)		X		X		X	X		X
N  -HOMe-dAdo (blood)		X		X		X	X		X
N  -ethylidene-dGuo (blood)		X		X		X	X		X
Total Nicotine Equivalents (urine)		X		X		X	X		X
Creatinine (urine)		X		X		X	X		X
q-PADDA (oral cells)		X		X		X	X		X
Exhaled breath CO	X	X	X	X	X	X	X		X
Pulmonary Function		X		X		X	X		X
Pregnancy Test	X	X	X	X	X	X	X		X
Saliva Sample		X		X		X	X		X

### Biomarkers of Toxicant Exposure

At visits where specimens are collected, participants will complete the Biomarker modifier questionnaire (used extensively in [name] current biomarker studies, a measure of factors that may moderate biomarkers of exposure and effect) which includes items that examine: a) tobacco smoke exposure at

### Examination of First and Second Generation E-cigarettes

[figure not shown]
home, work and socially; b) frequency of alcohol and other drug use; c) perceived stress; d) recent respiratory symptoms; and e) current medications. Most biomarkers of exposure proposed in this study have been analyzed extensively in [name] laboratory. Methods for the analyses are described in the literature, and [name] possesses the expertise and laboratory capacity to conduct these analyses. The collected urine samples will be aliquoted into 5-mL cryovials, and each vial will be labeled with a unique ID encoding the study, subject, sample collection time-point, and the type of assay. Aliquots will be frozen at -20 °C until analyses are conducted. Saliva samples (up to 2-3 mL will be obtained to analyze for cotinine levels. We will also save additional aliquots for potential future analyses of biomarkers of exposure to other constituents identified in this Aim, or other biomarkers that may be developed over time. Blood samples will be collected into 'purple top' blood collection vacutainer tubes, and plasma, red blood cells, and buffy coat will be separated by centrifugation. Buffy coat (used to isolate DNA), plasma, and red blood cells will be stored at -80 °C for potential future studies. Urinary total NNN and total NNAL. Exposure to NNK—an accepted cause of lung cancer in smokers—is measured by urinary total 4-(methylnitrosamino)-1-(3-pyridyl)-1butanol (NNAL), which is the sum of NNAL and its glucuronides. This biomarker has been widely applied in studies of smoking and cancer, and its relationship to lung cancer in smokers has been demonstrated. Exposure to NNN, a well-established esophageal and oral carcinogen, is measured by the sum of urinary NNN and its glucuronide, referred to as total NNN. Urinary NNN is strongly related to the incidence of esophageal cancer in smokers. Only relatively small levels of NNN and NNK, have been reported to be present in EC fluids and aerosols. However, according to both the published literature and our preliminary data ([name], unpublished), there can be significant variation in the content of these carcinogens in EC and potentially variations between G1 and G2 products. Total NNN and total NNAL will be analyzed by liquid chromatography (LC)-tandem mass spectrometry (MS/MS) using standard validated methods. Briefly, urine samples will be mixed with stable isotope-labeled internal standards ([pyridine-D4]NNN and [C6]NNAL) and treated with β-glucuronidase to release free NNN and NNAL from their glucuronides. The samples will be further purified by solid-phase extraction and analyzed by LC-MS/MS monitoring transitions *m/z* 178 → 148 for NNN, *m/z* 184 → 154 for [C6]NNN, *m/z* 210 → 93 NNAL and *m/z* 216 → 98 for [C6]NNAL. Urinary HPMA. Acrolein exposure is measured by urinary 3-hydroxypropyl mercapturic acid (HPMA). Acrolein was chosen because it is an intense irritant and lung toxicant, and a suggested lung carcinogen that is present in EC. It will be analyzed using a validated method, in which purified samples will be analyzed by LC-MS/MS in the APCI mode, monitoring *m/z* 220 → 91 for 2-HPMA and 3-HPMA, and *m/z* 223 → 91 for [D3]3-HPMA (internal standard). *N*-HOMe-dAdo, and *N*-ethylidene-dGuo in leukocyte DNA. Exposure to formaldehyde and acetaldehyde can be measured via the analysis of *N*-hydroxymethyl-deoxyadenosine (*N*-HOMe-dAdo) and *N*-ethylidene-deoxyguanosine (*N*-ethylidene-dGuo), respectively, in human leukocyte DNA.

## Examination of First and Second Generation E-cigarettes

Formaldehyde and acetaldehyde cause respiratory tumors in laboratory animals, and were chosen in this study because of the reports of their presence in EC aerosol at varying levels. These constituents are formed in EC aerosol via oxidation of humectants, such as glycerol and propylene glycol, which are present in EC fluids. This process depends on the heating voltage that is used in a given EC variety. Thus, due to higher heating temperatures and variable voltage options, G2s may yield higher levels of aldehydes as compared to G1s.  $N^6$ -HOMe-dAdo and  $N^2$ -ethylidene-dGuo will be analyzed as described. For  $N^6$ -HOMe-dAdo analysis, DNA isolated from buffy coat will be enzymatically hydrolyzed in the presence of NaBH3CN to convert the adduct to the more stable  $N^6$ -Me-dAdo. The hydrolysates will be further purified by solid-phase extraction, and analyzed by LC-MS/MS monitoring  $m/z$  266 → 150 for  $N^6$ -Me-dAdo and  $m/z$  271 → 155 for [N5] $N^6$ -Me-dAdo (internal standard). For  $N^2$ -ethylidene-dGuo analysis, enzymatic hydrolysis of DNA will be also performed in the presence of NaBH3CN to convert the adduct to  $N^2$ -ethyl-dGuo; the hydrolysate will be purified by solid-phase extraction; and the purified sample will be analyzed by LCMS/MS monitoring  $m/z$  296 → 180 for  $N^2$ -ethyl-dGuo and  $m/z$  301 → 185 for [N5] $N^2$ -ethyl-dGuo (internal standard). Urinary total nicotine equivalents. Total nicotine was chosen as a biomarker because it is the major known addictive constituent in tobacco and cigarette smoke, and is the key ingredient in EC. Nicotine content can greatly influence the category of users to which a given EC variety will appeal, and also affect the extent and pattern of EC use, thus driving exposures to other constituents in the given product. Analysis of these biomarkers will be conducted by gas chromatography (GC)-MS, using standardized methods. Urinary creatinine. Urinary creatinine will be analyzed to adjust biomarker levels for urine dilution. The analysis will be performed by Fairview-University Medical Center Diagnostic Laboratories (Minneapolis) with a Kodak Ektachem 500 chemistry analyzer. Exhaled Carbon monoxide (CO) will also be collected to corroborate self-reported complete substitution vs. not. *Note: in addition to human samples, [name] will also conduct comprehensive tobacco-related HPHC analysis on the vapor from a randomly selected subset of participant EC devices (10 from each arm). This serves two purposes: 1) to correlate constituent levels with biomarkers of exposure in study participants, and 2) to examine if any additional HPHCs should be included in our biomarker analysis.*

### Biomarkers of Toxicant Effect (DNA Damage)

Oral cells will be collected using a soft brush (CytoPak CytoSoft Brush, Medical Packing Corporation, CA). Briefly, study subjects will be instructed to rinse their mouths with tap water, then brush and twirl each cytobrush for 30 seconds over the specified regions of the mouth. Areas designated for collection will be the top and bottom “gutter” areas (each with a separate CytoBrush), between the upper gum line and the mucosa of upper lip and cheek, and between the lower gum line and the mucosa of lower lip and cheek on both sides of the mouth. DNA extraction will be performed using standard methods as we previously described. DNA damage will be quantified using q-PADDA (Fig. 6) in the transcribed strand (TS) and non-transcribed strand (NTS) of the *TP53* gene (oligonucleotides listed in Supplementary Table 1; Appendix) as we previously described. Briefly, a single non-cycled primer extension performed with a 5'-biotin-tagged primer and Vent exo- DNA polymerase identifies damaged nucleotides (Fig. 6, inverted triangles). The non-cycled primer extension generates a pool of highly specific biotin-tagged extended products (EP), each of them derived from one strand of a single DNA molecule. Each EP has a stop

**Fig. 6.** Schematic representation of q-PADDA.

## Examination of First and Second Generation E-cigarettes

(asterisk), which represents replicative arrest by a damaged nucleotide, or nick. After several purification steps, the extended single-stranded products will be re-quantification (q-PADDA). Real-Time PCR reactions will be carried out in a CFX96 Real-Time PCR system in a 10  $\mu$ l final volume with SsoAdvanced™ SYBR® Green Supermix (Bio-Rad), 0.3  $\mu$ M of each oligo, and 1.5/100 of total extended product pool. The PCR conditions will be: 95  $^{\circ}$ C, 3 min; 40 cycles (95  $^{\circ}$ C, 12 sec; 62  $^{\circ}$ C for TS and 61  $^{\circ}$ C for NTS, 2 min). Samples will be amplified with two oligo sets for each strand-specific area to be analyzed. One set amplifies the targeted fragment (~ 700 bp) under analysis (damage template), while the other set amplifies a reference (~ 50 bp) immediately 5' to the primer used for the initial primer-extension (undamaged template). Each sample will be assayed in at least three independent experiments. To analyze differences in amplification efficiency between samples, a threshold value on early exponential phase will be used. Damage will be analyzed using the  $2^{(\Delta C_t)} - 1$  method, or related to a standard curve for absolute quantification. Lesion frequency will be estimated using the Poisson equation  $n = -\ln(o)$ .

**Other Biomarkers of Effect:** Using a spirometer, a trained technician will measure Pulmonary functioning including, forced expiratory volume (FEV1), forced vital capacity (FVC), and FEV1/FVC.

## E. Statistical Methods

### Power Analysis

Complete substitution between LWD vs. HWD products is the primary outcome of the study, as rate of product substitution will likely drive the outcomes for all of the other aims; thus, we will estimate power for the proposed study based on this outcome at the 3-month follow-up. There are no direct data available on which we can base sample size estimates for the proposed study. The closest estimate for the LWD arm was based on the 3-month, 7-day point prevalence abstinence rate for the nicotine EC (21.5%); however, as smokers in this study were motivated to quit smoking, set a quit date, and were provided cessation counseling, we conservatively estimate that the percent of complete substitution will be lower in the LWD group (15%). For the HWD group, we will assume a substitution rate of 30% based on the 2-month abstinence rate for HWD products found in the only prospective trial of HWD use. As such, a total of 453 patients (151/group) will be enrolled into the study. This sample size will provide about 80% power to detect a 15% difference in complete substitution between LWD and HWD groups for a two-sided .05 level chi-squared test. In the sample size calculation, we assume the complete substitution rates are 15% and 30% for the LWD and HWD groups. Our estimates of sample size adjust for attrition rates of 20% in each arm. These attrition rates are a conservative estimate based on [name] previous research. We are confident that with a total sample size of 453 participants (n=363 after accounting for attrition), we will have adequate power to test our primary aim. It is important to note that this sample size is deliberately conservative, as it does not assume the availability of repeated outcome measures that will be taken throughout the study. By choosing models that utilize longitudinal data, we will be increasing the power to detect differences between arms.

### Data Analytic Plan

Statistical analyses will be performed using SAS 9.2 or later. P-values less than .05 will be considered statistically significant. Baseline demographics and smoker characteristics will be summarized by groups (LWD, HWD, and UBC). Continuous variables will be presented as mean $\pm$ SD and compared among 3 groups using ANOVA test. Categorical variables will be presented as counts and proportions and compared among 3 groups using the chi-squared test.

## Examination of First and Second Generation E-cigarettes

**Aim 1:** The focus of aim 1 is the examination of differential levels of (Hyp 1a) substitution between LWD and HWD, and (Hyp 1b) number of cigarettes smoked and nicotine dependence between G1, G2 and control. *Hypothesis 1a:* Complete substitution rates, at the end of the Product Trial Phase (3 months) and at both Surveillance Phase Visits (6 and 12 months), will be compared between LWD and HWD arms using multiple logistic regression models. If necessary, models will adjust for baseline variables such as age, gender, number of cigarettes per day and/or randomization stratification factors. The GEE model will be performed for the repeated measure analysis of complete substitution rate across multiple visits.

*Hypothesis 1b:* If needed, we will apply a normalizing transformation to the response measure (e.g., taking the logarithm of cigarettes per day) before proceeding with the analysis, as a means of removing the effects of potential outliers. A single linear mixed effects regression model will be used to simultaneously estimate the product arm effects on outcomes (i.e., cigarettes per day, nicotine dependence, motivation to quit smoking/nicotine) at 1, 3, 6 and 12-month follow-ups, with a subject-specific intercept included to account for within-subject correlation in the outcome over time. We will control for baseline value of the outcome and potential confounders (including any variables not equally distributed between groups). Product arm will be coded using two dummy variables to account for the three product arms. Modeling is done using a likelihood-based approach and thus makes use of all available data (on the ITT sample) to produce consistent estimates of the regression parameters.

**Aim 2:** The focus of aim 2 is the examination of changes over time in biomarkers of toxicant exposure (Hyp 2a) between LWD, HWD and UBC, and (Hyp 2b) among LWD vs. HWD users who completely switch.

*Hypothesis 2a:* The biomarker outcome measures analyzed will include mean levels of specific biomarkers at all follow-up time points. The analysis of biomarkers of toxicant exposure will be analyzed similar to outcome variables in Hypothesis 1b. Again mixed effects models will be used for analysis and resulting contrast estimates comparing group effects over time will be used as measure of effect. We will again apply a normalization transformation but will also include potential confounding factors measured in the

*Biomarker Modifier Questionnaire* in the model. *Hypothesis 2b:* Similar analyses to Hypothesis 2a will be performed but only among the subset of LWD and HWD users who completely switch.

**Aim 3:** The focus of Aim 3 is the examination of changes over time in biomarkers of toxicant effect (Hyp 3a) between LWD, HWD and UBC, and (Hyp 3b) amongst LWD vs. HWD users who completely switch. For Aim 3 (Hypothesis 3a and IRB NUMBER: 6379 3b), we will run the same analyses as in Aim 2, but the biomarker outcome measures analyzed will include mean levels of DNA damage and pulmonary functioning at all follow-ups.

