#### Aim 1:

**To assess the effect of provision of LWD vs. HWD on product switching/substitution, abuse liability, number of cigarettes smoked, and perceived nicotine dependence.** *Hypothesis 1a: Complete product substitution (vs. partial or no substitution) will occur at a significantly higher rate among smokers randomized to HWD products compared to those randomized to LWDs at 12, 26, and 52-week follow-ups. Hypothesis 1b: Compared to those randomized to UBC, LWD and HWD participants will smoke fewer cigarettes per day, have lower product abuse liability and lower perceived nicotine dependence.*

**Aim 2: To evaluate changes in biomarkers of harmful tobacco constituent exposure among participants assigned to LWD, HWD, and UBC.** *Hypothesis 2a: The degree of changes in exposure will be directly associated with the degree of substitution with EC—greater levels of substitution will confer a larger decrease in exposure to harmful constituents. Hypothesis 2b: Among those who completely substitute ECs for conventional cigarettes, LWD users (vs. HWD) will have significantly lower levels of biomarkers of exposure.*

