## Examination of First and Second Generation E-cigarettes

**Aim 3: To evaluate changes in biomarkers of toxicant effect among participants assigned to G1, G2, and UBC.** *Hypothesis 3a: The degree of changes in biomarkers of effect (levels of DNA damage-markers indicative of increased cancer risk) will be directly associated with the degree of substitution—greater levels of substitution will confer a larger reduction in levels of DNA damage. Hypothesis 3b: Among those who completely substitute ECs for conventional cigarettes, LWD users (vs. HWD) will have significantly reduced markers indicative of increased cancer risk.*

***Our team is uniquely suited to conduct this investigation. Understanding how smokers use ECs as they transition away from smoking and carefully examining their health effects is critically important. This novel study will contribute knowledge urgently needed by the FDA and health officials to effectively regulate ECs in a way that best serves public health.***

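### Hypotheses 2b and 3b claim a significant LWD–HWD biomarker difference among switchers, but several biomarkers are analysed at several visits, each at p<.05, with no rule for what decides the claim

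*Combined protocol and SAP*

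**What the plan says.** All references are to the Combined protocol and SAP.

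- **Specific Aims.** Hypothesis 2b states that, among complete switchers, "LWD users (vs. HWD) will have significantly lower levels of biomarkers of exposure". Hypothesis 3b states that "LWD users (vs. HWD) will have significantly reduced markers indicative of increased cancer risk". Each is a single directional claim over a group of markers.
- **Section E, Data Analytic Plan, general rule.** "P-values less than .05 will be considered statistically significant". No exception or adjustment follows.
- **Section E, Aim 2.** Under Hypothesis 2a: "The biomarker outcome measures analyzed will include mean levels of specific biomarkers at all follow-up time points". Hypothesis 2b repeats this in the LWD and HWD participants who switch completely. The effect measure is a contrast of group effects over time from a mixed model. The text does not fix whether that is one contrast per marker or one per visit.
- **Section E, Aim 3.** The Aim 2 analyses are repeated, but "the biomarker outcome measures analyzed will include mean levels of DNA damage and pulmonary functioning at all follow-ups".
- **Section B, Innovation.** Lung function is called a secondary health outcome. The Aim 3 analysis text does not use that ranking.
- **Section D, Biomarkers of Toxicant Exposure.** Emission tests on a sample of devices serve in part "to examine if any additional HPHCs should be included in our biomarker analysis".
- **Section E, Power Analysis.** Complete substitution is the primary outcome and the only one powered.

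**The concern.** Nothing in the plan says what result would support 2b or 3b. With several markers, several visits and one threshold for all, a single chance result in one marker at one visit could be reported as a significant toxicological difference between devices. The abstract and Specific Aims present the trial as part of the evidence for product-specific regulation, so such a result could carry weight.

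The switcher groups are small, so a chance finding would also look large. With about 18 and 36 switchers, an unadjusted single-visit comparison reaches p<.05 only at an observed difference of 2.007 × √(1/18 + 1/36) = 0.58 SD or more.

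**Working it through.** **1. The plan's own figure.** Inputs from Power Analysis: 15% versus 30%, 80% power, "two-sided .05 level chi-squared test", 20% attrition.

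n per arm = [1.960·√(2·0.225·0.775) + 0.8416·√(0.15·0.85 + 0.30·0.70)]² / 0.15² = (1.157 + 0.489)² / 0.0225 ≈ 120.5, so 121.

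121/0.8 = 151.25, against the stated 151. Power at 121 per arm is 80.2%. The stated figure is reproduced. The documents give no family-wise error rate for Aims 2 and 3, so there is no plan figure to compare with what follows.

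**2. Size of the switcher subsets at 3 months.** 0.15 × 121 ≈ 18 LWD; 0.30 × 121 ≈ 36 HWD.

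**3. Number of tests.**
- 2b: six laboratory exposure markers are described in section D (total NNAL, total NNN, HPMA, the formaldehyde and acetaldehyde DNA adducts, total nicotine equivalents).
- 3b, read as DNA damage: two q-PADDA measures (transcribed and non-transcribed strand of *TP53*).
- Visits: four follow-ups, from the time points in the Hypothesis 1b model. Table 3 is consistent with this as far as its columns can be read.

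**4. Check by closed form (independent tests).** Six tests: 1 − 0.95⁶ = 26.5%. Two tests: 1 − 0.95² = 9.75%.

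**5. Correlated tests.** Multivariate normal z-statistics were simulated with no LWD–HWD difference in any marker. The critical value was |z| > 1.96. Assumed correlations were 0 to 0.8 between markers (0 gives the upper end of each range) and 0.5 between visits. Two-sided testing of biomarkers is also an assumption, since the plan states sidedness only for the primary test.

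| Family | Any false p<.05, two-sided | False result in predicted direction |
|---|---|---|
| 2b, 6 markers, one contrast each | 14–26% (21% at 0.5) | 7–14% |
| 2b, 6 markers × 4 visits | 38–64% (53% at 0.5) | 19–39% |
| 3b, 2 strands, one contrast each | 8–10% (9% at 0.5) | 4–5% |
| 3b, 2 strands × 4 visits | 23–29% (27% at 0.5) | 12–15% |

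The nominal values are 5% two-sided and 2.5% in one direction.

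**6. Sensitivity to the marker count, at correlation 0.5.** HPMA has no row in Table 3; without it, five markers give 18% and 48%. Exhaled CO is named as an exposure measure under Innovation; with it, seven markers give 23% and 58%. The second analysis described under Missing Data is not counted.

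**7. Effect and cost of an adjustment.** Bonferroni over six contrasts (.05/6 = .0083) gives 4.9% if independent and 4.1% at correlation 0.5; Holm has the same error rate when no marker differs. For power, take a t-test with 18 versus 36. A standardised difference of about 0.82 has 80% power at .05 and about 54% at .0083. Restoring 80% at .0083 needs about 1.04.

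**The case against.** The strongest defence is that these hypotheses sit below a named primary outcome. Power Analysis powers only substitution: "This sample size will provide about 80% power to detect a 15% difference in complete substitution between LWD and HWD groups". Nowhere does the plan call Aims 2 and 3 confirmatory, and unadjusted testing of lower-ranked hypotheses is common. This stands as far as ranking goes. But the hypotheses predict a *significant* difference and carry no exploratory label, and the ranking does not say how they would be decided.

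Second, no text says that one marker at one visit suffices. The hypotheses speak of biomarkers in the plural, and one contrast per marker is as natural a reading of the analysis text as one per visit. This also stands. Both readings are shown for that reason, and the lower one still exceeds the nominal rate.

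Third, a null for every marker is a worst case. Section D reports small nitrosamine levels in e-cigarette products but also possible variation between generations, and it expects higher aldehyde yields from HWD. This is fair: the figures apply where there is no difference and do not predict that there is none.

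A reader might extend the point to the arm contrasts under 2a and 3a, where error rates of 44–85% can be computed for six markers and three pairwise contrasts at correlation 0.5. The documents do not support that. As worded, 2a and 3a concern degree of substitution. Those rates also require no difference from UBC, whereas under Measures the markers were chosen for properties such as separating smokers from nonsmokers or falling on cessation.

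The emission tests could add markers on the basis of device data, not participants' p-values. That calls for a label and is not evidence of selective testing.

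**Conclusion.** The point holds for Hypotheses 2b and 3b. The plan has no decision rule for either claim, and applying p<.05 to each test inflates the chance of a false device difference. For 2b the rate is about 14–26% (one contrast per marker) or 38–64% (per visit), and roughly half that in the predicted direction. For 3b on the two DNA-damage strands it is about 8–10% or 23–29%. All of this assumes two-sided tests, no true difference, marker correlations of 0–0.8 and a visit correlation of 0.5.

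A reader might infer a single headline of 20–50% for all the biomarker hypotheses. That would overstate it: such a range suits 2b only, counts both directions and depends on the assumed correlations. For 3b, 18% and 48% (correlation 0.5) arise only if the three spirometry measures are added to the two strands, and spirometry is not part of the 3b claim.

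The substitution analysis is unaffected. This is a point the sponsor should act on; it does not undermine the trial.

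**What to change.** In the Data Analytic Plan, Aims 2 and 3:

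1. Label the 2b and 3b analyses secondary or exploratory.
2. Give a closed list of biomarkers, and report the LWD–HWD estimate with its confidence interval for every listed biomarker and visit.
3. State that no significant device difference will be claimed from individual unadjusted p-values, and reword 2b and 3b to match.
4. Keep spirometry secondary, as under Innovation, and label exploratory any biomarker added after the emission tests.

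If the sponsor wants to keep the claim of significantly lower or reduced levels, prespecify one LWD–HWD contrast per biomarker, for example at week 12 or averaged over follow-up. Apply Holm at .05 across the closed list within each hypothesis. Weeks 26 and 52 stay in the model and are reported, so the long-term purpose of the Surveillance Phase is kept.

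**Cost.** The first route needs only a change of wording and a more modest label. The second loses real power: about 80% falls to about 54% for a marker that must meet .0083 with 18 versus 36 switchers. Neither route removes the selection bias from comparing subsets defined by switching after randomisation. That limitation should be stated alongside the results.

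### Hypotheses 2a and 3a predict an association with degree of substitution, but the plan analyses both only by contrasts between randomised arms, which do not test it.

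*Combined protocol and SAP*

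**What the plan says.** Section A (Specific Aims) words Hypothesis 2a as "The degree of changes in exposure will be directly associated with the degree of substitution with EC". Hypothesis 3a says "greater levels of substitution will confer a larger reduction in levels of DNA damage". Both concern what participants do with the product, on a graded scale. Hypothesis 1a names three levels of that scale: "Complete product substitution (vs. partial or no substitution) will occur at a significantly higher rate".

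Section E (Data Analytic Plan) gives Aim 2 a different focus: "changes over time in biomarkers of toxicant exposure (Hyp 2a) between LWD, HWD and UBC". On method it says "The analysis of biomarkers of toxicant exposure will be analyzed similar to outcome variables in Hypothesis 1b". In the 1b model, "Product arm will be coded using two dummy variables to account for the three product arms". For 2a, "resulting contrast estimates comparing group effects over time will be used as measure of effect". Aim 3 repeats the Aim 2 analyses with DNA damage and pulmonary function as outcomes, and 3a is again described as a comparison of the three arms. Hypotheses 2b and 3b are examined "only among the subset of LWD and HWD users who completely switch".

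The Outcome Measures section defines complete substitution only: at most one cigarette in the 7 days, exhaled CO below 4 ppm, and reported EC use in the same 7 days. Partial substitution is not defined. Graded data are nevertheless collected: 7-day Timeline Follow-Back for all nicotine products, and diary entries for cigarettes per day and EC use.

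**The concern.** An arm contrast estimates the effect of being assigned a product. Hypotheses 2a and 3a concern how biomarker change varies with the amount of substitution, both within and across arms. These are different quantities. A null contrast would not refute 2a or 3a, and a significant one would not show that benefit rises with substitution.

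This matters because the Power Analysis section expects substitution to drive the outcomes of the other aims. The plan therefore treats substitution as the mechanism but never estimates its relation to the biomarkers. With no graded measure fixed in advance, any later dose-response analysis would be post hoc in its choice of measure and cut-points.

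**Working it through.** **1. Hypothesis against model**

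| | Hypothesis as stated | Predictor of interest in the plan | Substitution as a predictor? |
|---|---|---|---|
| 2a | Exposure change against degree of substitution | Arm (two dummies) | No |
| 3a | DNA-damage change against degree of substitution | Arm (same analysis as Aim 2) | No |
| 2b, 3b | LWD against HWD in complete switchers | Arm, within that subset | Only as the filter; its degree does not vary |

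The covariates added for 2a come from the Biomarker Modifier Questionnaire: smoke exposure, alcohol and drugs, stress, respiratory symptoms and medications. None of these is substitution.

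**2. The plan's own power figure**

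The plan states about 80% power for complete substitution at 15% against 30%, with 20% attrition. The analysed number is 453 × 0.80 = 362.4, which the plan gives as 363, or 121 per arm. With pooled variance and no continuity correction:

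- mean rate = 0.225
- z = [0.15 × √121 − 1.96 × √(2 × 0.225 × 0.775)] / √(0.15 × 0.85 + 0.30 × 0.70) = (1.650 − 1.157) / 0.581 = 0.85
- power = 80.2%

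The figure reproduces, but it concerns 1a only. No power is stated for 2a or 3a.

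**3. What an arm contrast measures**

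Let complete substitution shift the biomarker by β, let p be the proportion substituting, and let δ be any other effect of the assigned device. The mean change in an arm is βp + δ, so

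HWD − LWD = β(0.30 − 0.15) + (δ_HWD − δ_LWD).

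The contrast mixes β with device effects. Two cases on assumed effects show the consequence. Only the 15% and 30% rates come from the documents; UBC is set at 0%, residual SD is 1, and LWD has no device effect.

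- **Case A, association present:** β = −1 SD and δ_HWD = +0.15 SD. The positive sign follows the plan's own expectation that HWDs may deliver more toxicants. HWD − LWD = (−0.30 + 0.15) − (−0.15) = 0. HWD − UBC = −0.30 + 0.15 = −0.15.
- **Case B, association absent:** β = 0 and δ_HWD = −0.5 SD. Both HWD contrasts equal −0.5.

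Simulation used 2,000 trials per case, 121 per arm, one visit and least squares:

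| | HWD − LWD: mean, rejection | HWD − UBC: mean, rejection | Substitution term: mean, rejection |
|---|---|---|---|
| A | 0.00, 5.8% | −0.15, 19% | −1.00, 100% |
| B | −0.50, 97% | −0.50, 98% | 0.00, 4% |

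The HWD contrasts give the wrong answer about the association in case B, and HWD − LWD carries no information about it in case A.

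**4. What a substitution term must contain**

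Hypothesis 2a concerns substitution with ECs, not cutting down as such. Two simple scores were compared by simulation on assumed effects with a true slope of 1. If only EC users benefit from reduction, percent reduction with a separate additive EC term gives 0.82, while reduction scored as zero in non-EC users gives 0.99. If reduction alone matters, the same two scores give 0.99 and 0.67. Neither is right in general, so the measure must combine reduction with EC use explicitly.

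**The case against.** The best defence is that Aims 2 and 3 are themselves titled as changes among participants assigned to each product. Randomised contrasts answer that question without confounding, which a substitution model cannot claim. If substitution differs by arm as expected, the contrasts also carry indirect evidence on 2a and 3a. All of this stands. It justifies keeping the contrasts, but it does not make them a test of the association.

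It could also be argued that group in the 2a sentence means substitution group, or that the word similar leaves room for a further term. The statements of focus for Aims 2 and 3 name LWD, HWD and UBC, and no substitution term appears elsewhere. The baseline-summary paragraph also uses group for arm, but it concerns baseline tables only and adds little.

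Three stronger readings are tempting and are not supported:

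- **That the plan models no graded smoking measure at all.** Cigarettes per day is a modelled outcome under 1b. What is missing is a graded substitution measure as a predictor in Aims 2 and 3.
- **That the trial is underpowered for 2a and 3a.** The documents give no biomarker effects or SDs. On assumed effects at one visit with 121 per arm, arm-contrast power runs from 6% to 99.9%. With a 1 SD shift in complete switchers only, it is 20.5% (LWD against UBC), 60.3% (HWD against UBC) and 19.0% (HWD against LWD). If everyone else in the EC arms gets half that shift, it is 99.3%, 99.9% and 8.8%. These figures also ignore the planned repeated measures and baseline adjustment. They illustrate and do not support the point.
- **That the arm contrasts are invalid.** They are valid for what they estimate.

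**Conclusion.** The point holds as a mismatch between hypothesis and analysis, and it should be fixed. It rests on reading Section A against Section E, not on any power figure. Two secondary hypotheses would be left without a test; the primary outcome, its sample size and the randomised comparisons are untouched.

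Cases A and B need only that a device can affect biomarkers by a route other than substitution, which the plan itself anticipates for HWDs. Their effect sizes are assumed. The one-visit simulations do not validate the mixed model proposed below.

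**What to change.** For 2a and 3a, add to the existing mixed model a prespecified visit-level degree-of-substitution term, built from the 7-day Timeline Follow-Back and the diary.

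- **Measure.** Combine cigarette reduction with EC use over the same period, so that cutting down without ECs is distinguished from substitution. Examples are none/partial/complete categories with a stated cut-point, or percent reduction with an EC-use-by-reduction interaction. If exhaled CO helps define the category, do not also use it as an outcome in that model.
- **Model.** Keep arm and baseline biomarker, and adjust for baseline cigarettes per day and dependence. State whether the slope is between-person or within-person, since a random-intercept model with a time-varying predictor otherwise blends the two.
- **Rules to fix in advance.** Specify the handling of UBC participants, of people using neither product, and of missing substitution data; the weighting in the Missing Data section is described for missing responses. Fix these before the substitution-biomarker analysis is run. About half the sample (220) was already recruited, and the documents do not say whether assays have begun.
- **Reporting.** Label the result observational and secondary. Name the three-arm contrasts as the intention-to-treat analysis of Aims 2 and 3.

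The alternative is to reword 2a and 3a as between-arm hypotheses and draw no conclusion about degree of substitution from arm contrasts.

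**Cost.** No new data or visits are needed. The first option adds one non-randomised model per biomarker, open to confounding, and further secondary tests at .05. The second changes only text but gives up the dose-response question.
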